XXXXXXXXXX.sas, DMMMMYYYY:HHMM

TABLE 14.3.15  
 Clinical Chemistry - Other - Actual and Change from Baseline Results

<PAGE 2 FORMAT>

Tx #	Parameter Name (SI Units)	Actual						Change from Baseline					
		n	Mean	SD	Med	Min	Max	n	Mean	SD	Med	Min	Max
Tx 2 (N=X)													
Day 1	Glucose (units)	X	XX	XX	XX	XX	XX	X	XX	XX	XX	XX	XX
	Total Protein (units)	X	XX	XX	XX	XX	XX	X	XX	XX	XX	XX	XX
	Calcium (units)	X	XX	XX	XX	XX	XX	X	XX	XX	XX	XX	XX
	Carbon Dioxide (units)	X	XX	XX	XX	XX	XX	X	XX	XX	XX	XX	XX
Week 1	Glucose (units)	X	XX	XX	XX	XX	XX	X	XX	XX	XX	XX	XX
	Total Protein (units)	X	XX	XX	XX	XX	XX	X	XX	XX	XX	XX	XX
	Calcium (units)	X	XX	XX	XX	XX	XX	X	XX	XX	XX	XX	XX
	Carbon Dioxide (units)	X	XX	XX	XX	XX	XX	X	XX	XX	XX	XX	XX
Etc.													

Note: Day 1 assessments were obtained during 24 hours post-transplant during the Treatment Phase (in-clinic).

XXXXXXXXXX.sas, DDMMYYYY:HHMM

TABLE 14.3.15  
 Clinical Chemistry - Other - Actual and Change from Baseline Results

<PAGE 3 FORMAT>

Tx #	Parameter Name (SI Units)	Actual						Change from Baseline					
		n	Mean	SD	Med	Min	Max	n	Mean	SD	Med	Min	Max
Tx 3 (N=X)													
Day 1	Glucose (units)	X	XX	XX	XX	XX	XX	X	XX	XX	XX	XX	XX
	Total Protein (units)	X	XX	XX	XX	XX	XX	X	XX	XX	XX	XX	XX
	Calcium (units)	X	XX	XX	XX	XX	XX	X	XX	XX	XX	XX	XX
	Carbon Dioxide (units)	X	XX	XX	XX	XX	XX	X	XX	XX	XX	XX	XX
Week 1	Glucose (units)	X	XX	XX	XX	XX	XX	X	XX	XX	XX	XX	XX
	Total Protein (units)	X	XX	XX	XX	XX	XX	X	XX	XX	XX	XX	XX
	Calcium (units)	X	XX	XX	XX	XX	XX	X	XX	XX	XX	XX	XX
	Carbon Dioxide (units)	X	XX	XX	XX	XX	XX	X	XX	XX	XX	XX	XX
Etc.													

Note: Day 1 assessments were obtained during 24 hours post-transplant during the Treatment Phase (in-clinic).

XXXXXXXXXX.sas, DDMMYYYY:HHMM

TABLE 14.3.16  
 Immunology - PRA - Actual and Change from Baseline Results

Tx #	PRA (%)	Actual						Change from Baseline					
		n	Mean	SD	Med	Min	Max	n	Mean	SD	Med	Min	Max
Tx 1 (N=X)													
Baseline[1]	Class I	X	XX	XX	XX	XX	XX						
	Class II	X	XX	XX	XX	XX	XX						
Week 3	Class I	X	XX	XX	XX	XX	XX	X	XX	XX	XX	XX	XX
	Class II	X	XX	XX	XX	XX	XX	X	XX	XX	XX	XX	XX
Week 12	Class I	X	XX	XX	XX	XX	XX	X	XX	XX	XX	XX	XX
	Class II	X	XX	XX	XX	XX	XX	X	XX	XX	XX	XX	XX
Etc.													
Tx 2 (N=X)													
Week 3	Class I	X	XX	XX	XX	XX	XX	X	XX	XX	XX	XX	XX
	Class II	X	XX	XX	XX	XX	XX	X	XX	XX	XX	XX	XX
Week 12	Class I	X	XX	XX	XX	XX	XX	X	XX	XX	XX	XX	XX
	Class II	X	XX	XX	XX	XX	XX	X	XX	XX	XX	XX	XX
Etc.													
Tx 3 (N=X)													
Week 3	Class I	X	XX	XX	XX	XX	XX	X	XX	XX	XX	XX	XX
	Class II	X	XX	XX	XX	XX	XX	X	XX	XX	XX	XX	XX
Week 12	Class I	X	XX	XX	XX	XX	XX	X	XX	XX	XX	XX	XX
	Class II	X	XX	XX	XX	XX	XX	X	XX	XX	XX	XX	XX
Etc.													

[1] Baseline is always the last value before the initial transplant.

XXXXXXXXXXXX.sas, DDMMYYYY:HHMM

Table 14.3.17  
 Urine Albumin - Shifts from Normal at Baseline to Abnormal after Transplants

Tx Sequence	Baseline [1] Status	Patients at Baseline	Abnormal[2] at Week 8/9 n (%)	Abnormal at Week 20 n (%)	Abnormal at Week 40 n (%)	Abnormal at Week 52 n (%)
Tx 1 (N=X)	Normal	XX	X (X)	X (X)	X (X)	X (X)
	Microalbuminuria (30-300 mg/day)	XX	X (X)	X (X)	X (X)	X (X)
Tx 2 (N=X)	Normal		X (X)	X (X)	X (X)	X (X)
	Microalbuminuria (30-300 mg/day)		X (X)	X (X)	X (X)	X (X)
Tx 3 (N=X)	Normal		X (X)	X (X)	X (X)	X (X)
	Microalbuminuria (30-300 mg/day)		X (X)	X (X)	X (X)	X (X)
Total New Onset Abnormal up to 1 Year after Last Tx			XX (XX)			

Note: All percentages are based upon the number of patients at baseline for the specific baseline status.  
 [1] Baseline is always the value before the initial transplant.  
 [2] For patients with normal baseline, new onset of microalbuminuria (>30 mg/day) is counted as "abnormal"; for those with baseline microalbuminuria, new onset of overt albuminuria (> 300 mg/day) is counted as "abnormal".

XXXXXXXXXX.sas, DMMMMYYY:HHMM

Table 14.3.18  
 Listing of Treatment-Emergent Laboratory Abnormalities and PCS Results

# of Tx Received	ID	Age (yrs.)	Assessment	Laboratory Parameter	Normal		Abnormal Result	PCS Criteria (if any)	PCS Result? (Y/N)	Baseline Result
					LLN	ULN				
1 Tx	XXX	XX	XXXXXXXXX	XXXXXXXXXX	XXX	XXX	XXXXXX	XXXXXXXXX	X	XXXXXX
				XXXXXXXXXX	XXX	XXX	XXXXXX	XXXX	X	XXXXXX
				XXXXXXXXXX	XXX	XXX	XXXXXX			XXXXXX
			XXXXXXXXXX	XXXXXXXXXX	XXX	XXX	XXXXXX	XXXX	X	XXXXXX
			XXXXXXXXXX	XXXXXXXXXX	XXX	XXX	XXXXXX	XXXX	X	XXXXXX
			XXXXXXXXXX	XXXXXXXXXX	XXX	XXX	XXXXXX	XXXX	X	XXXXXX
2 Tx	XXX	XX	XXXXXXXXX	XXXXXXXXXX	XXX	XXX	XXXXXX	XXXXXXXXX	X	XXXXXX
				XXXXXXXXXX	XXX	XXX	XXXXXX	XXXX	X	XXXXXX
Etc.										

Note: PCS = Potentially Clinically Significant

XXXXXXXXXXXX.sas, DDMMYY:HHMM

TABLE 14.3.19

Vitals Signs - Systolic Blood Pressure (mmHg) - Actual and Change from Baseline Results

# of Tx Received	Assessment Time	Actual						Change from Baseline					
		n	Mean	SD	Med	Min	Max	n	Mean	SD	Med	Min	Max
1 Tx (N=XX)	Baseline[1]	X	XX	XX	XX	XX	XX						
	Day 1[2]												
	15 min	X	XX	XX	XX	XX	XX	X	XX	XX	XX	XX	XX
	30 min	X	XX	XX	XX	XX	XX	X	XX	XX	XX	XX	XX
	45 min	X	XX	XX	XX	XX	XX	X	XX	XX	XX	XX	XX
	1 hr												
	etc.	X	XX	XX	XX	XX	XX	X	XX	XX	XX	XX	XX
	Week 1	X	XX	XX	XX	XX	XX	X	XX	XX	XX	XX	XX
	etc.	X	XX	XX	XX	XX	XX	X	XX	XX	XX	XX	XX
2 Tx's (N=XX)													
Etc.													

[1] Baseline is always the value before the initial transplant.

[2] Day 1 assessments were obtained during 24 hours post-transplant during the Treatment Phase (in-clinic).

XXXXXXXXXX.sas, DDMMYYYY:HHMM

TABLE 14.3.20

Vitals Signs - Diastolic Blood Pressure (mmHg) - Actual and Change from Baseline Results

# of Tx Received	Assessment Time	Actual						Change from Baseline					
		n	Mean	SD	Med	Min	Max	n	Mean	SD	Med	Min	Max
1 Tx (N=XX)	Baseline[1]	X	XX	XX	XX	XX	XX						
	Day 1[2]												
	15 min	X	XX	XX	XX	XX	XX	X	XX	XX	XX	XX	XX
	30 min	X	XX	XX	XX	XX	XX	X	XX	XX	XX	XX	XX
	45 min	X	XX	XX	XX	XX	XX	X	XX	XX	XX	XX	XX
	1 hr	X	XX	XX	XX	XX	XX	X	XX	XX	XX	XX	XX
	etc.												
	Week 1	X	XX	XX	XX	XX	XX	X	XX	XX	XX	XX	XX
	etc.												
2 Tx's (N=XX)													
Etc.													

[1] Baseline is always the value before the initial transplant.

[2] Day 1 assessments were obtained during 24 hours post-transplant during the Treatment Phase (in-clinic).

XXXXXXXXXX.sas, DDMMYYYY:HHMM

TABLE 14.3.21  
 Vitals Signs - Heart Rate (beats/min) - Actual and Change from Baseline Results

# of Tx Received	Assessment Time	Actual						Change from Baseline					
		n	Mean	SD	Med	Min	Max	n	Mean	SD	Med	Min	Max
1 Tx (N=XX)	Baseline[1]	X	XX	XX	XX	XX	XX						
	Day 1[2]												
	15 min	X	XX	XX	XX	XX	XX	X	XX	XX	XX	XX	XX
	30 min	X	XX	XX	XX	XX	XX	X	XX	XX	XX	XX	XX
	45 min	X	XX	XX	XX	XX	XX	X	XX	XX	XX	XX	XX
	1 hr	X	XX	XX	XX	XX	XX	X	XX	XX	XX	XX	XX
	etc.												
	Week 1	X	XX	XX	XX	XX	XX	X	XX	XX	XX	XX	XX
	etc.												
2 Tx's (N=XX)													
Etc.													

[1] Baseline is always the value before the initial transplant.

[2] Day 1 assessments were obtained during 24 hours post-transplant during the Treatment Phase (in-clinic).

XXXXXXXXXX.sas, DDMMYYYY:HHMM

TABLE 14.3.22

Vitals Signs - Temperature (°F) - Actual and Change from Baseline Results

# of Tx Received	Assessment Time	Actual						Change from Baseline					
		n	Mean	SD	Med	Min	Max	n	Mean	SD	Med	Min	Max
1 Tx (N=XX)	Baseline[1]	X	XX	XX	XX	XX	XX						
	Day 1[2]												
	15 min	X	XX	XX	XX	XX	XX	X	XX	XX	XX	XX	XX
	30 min	X	XX	XX	XX	XX	XX	X	XX	XX	XX	XX	XX
	45 min	X	XX	XX	XX	XX	XX	X	XX	XX	XX	XX	XX
	1 hr	X	XX	XX	XX	XX	XX	X	XX	XX	XX	XX	XX
	etc.												
	Week 1	X	XX	XX	XX	XX	XX	X	XX	XX	XX	XX	XX
	etc.												
2 Tx's (N=XX)													
Etc.													

[1] Baseline is always the value before the initial transplant.

[2] Day 1 assessments were obtained during 24 hours post-transplant during the Treatment Phase (in-clinic).

XXXXXXXXXX.sas, DDMMYYYY:HHMM

TABLE 14.3.23  
 Listing of Vital Signs for Patients with PCS Treatment-Emergent Results

# of Tx Received	Subj. No.	Age (yrs.)	Timepoint	Vital Sign Parameter	PCS? (Y=yes)	Timepoint Value	Baseline Value
1 Tx	XXX	XX	Day 1 30 min	SBP (mmHg)		XX	XX
				SBP (mmHg)		XX	XX
				HR (beats/min)	Y	XX	XX
			etc.				
	XXX	XX	Week 1	SBP (mmHg)		XX	XX
				SBP (mmHg)		XX	XX
HR (beats/min)				Y	XX	XX	
		etc.					
2 Tx	Etc.						

Note: Potentially Clinically Significant (PCS) Criteria:

SBP: >180 mmHg and an increase of >=20 mmHg OR <90 mmHg and a decrease of >=20 mmHg from baseline

DBP: >105 mmHg and an increase of >=15 mmHg OR <50 mmHg and a decrease of >=15 mmHg from baseline

HR: >120 beats/min and an increase of >=15 beats/min OR <50 beats/min and a decrease of >=15 beats/min

XXXXXXXXXX.sas, DDMMYYYY:HHMM

TABLE 14.3.24  
 Electrocardiogram - Worsening from Baseline to 1 Year Post Last Transplant

# of Tx Received	Number (%) [1] of Patients Who Worsened [2]		
	Post- Transplant Assessment Time		
	Total	Week 20	Week 52
Total (N=X) Worsened	X (XX)		
1 Tx (N=X) Worsened	X (XX)	X (XX)	X (XX)
2 Tx (N=X) Worsened	X (XX)	X (XX)	X (XX)
3 Tx (N=X) Worsened	X (XX)	X (XX)	X (XX)

[1] The denominator is the corresponding number of patients in the leading column.

[2] Worsening is defined as a change from a rating of normal/abnormal not clinically significant on both of the pre-transplant assessments to abnormal clinically significant at the time point.

XXXXXXXXXX.sas, DDMMYYYY:HHMM

TABLE 14.3.25  
Listing of Patients with Treatment-Emergent ECG Abnormalities

# of Tx Received	Subj. No.	Age (yrs.)	Timepoint	ECG Abnormality Description
1 Tx	XXX	XX	Week 20	XXXXXXXXXXXXXXXXXXXXX
			etc.	
2 Tx	XXX	XX	Week 52	XXXXXXXXXXXXXXXXXXXXX
			etc.	

Total number of patients with at least one event: N = XX

---

XXXXXXXXXXXX.sas, DDMMYYYY:HHMM

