6.6.6 Early Post-Transplant Period (see Appendix Post-Transplant Orders)

After the islet transplant procedure, subjects will stay for a minimum of 24 hours in hospital with close monitoring in the UIC Hospital Transplant Unit (7W), offering intensive care unit equivalent conditions. Vital signs are monitored every 15 minutes for the first hour, then every 30 minutes for 4 hours, then every 4 hours thereafter until discharge. During the first 24 hours after islet transplantation, liver tests, amylase, lipase, and CBC will be monitored every 8 hours.

Starting at least 4 hours after the islet infusion, subjects will begin a series of treatments with low molecular weight heparin (enoxaparin sodium, Lovenox® 30 mg sc bid, which may be self-administered) for seven days. Hemoglobin will be monitored 3 times during the first week following the transplant procedure.

An ultrasound and Doppler evaluation of the portal system will be performed within 24 hours after each islet transplantation procedure to rule out the possibility of complication including portal thrombus or perihepatic hematoma. If portal vein thrombosis is encountered within a main right or left portal branch within the main portal vein (i.e., main portal vein, but not a segmental peripheral branch), this will be considered a serious adverse event (SAE). In case of portal thrombosis, the subject will receive therapeutic anticoagulation with heparin until reaching a therapeutic INR with oral anticoagulants for a period of 3 months. Ultrasound will be repeated until the portal vein thrombus is resolved.

Subjects will be discharged home 24 hours after transplant if afebrile, having stable hemoglobin, and provided post-transplant Doppler ultrasound is within normal limits. Subjects will be provided with contact information in the event of questions or adverse experiences following discharge.

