M/C ratio (random)		X	X	X						X					X					X			X
Sputum culture, sensitivity					#																		
Blood culture, sensitivity					#																		
Glucagon stimulation test	X									X						X							X
Mixed meal test		X														X							X
OGTT										X						X							X
IVGTT										X						X							X
ECG	X			X											X								X
Chest x-ray		X																					X
Abdominal ultrasound, Doppler		X				X																	
Cardiology Consult		X																					
CGMS		X																					X
Primary care	X																						X
Thyroid Ultrasound		X																					X

Visit A: screenings for inclusion

Visits 1 and 2 include 3 evaluations per week; Visit 3 includes 2 evaluations per week; Visits 4 to 7 include 2 evaluations per 2 week period (1 visit per week)

Vital signs: blood pressure, heart rate, respirations, temperature

CMP: comprehensive metabolic profile

CBC: complete blood count

BNP: B-type natriuretic peptide

Antibodies: anti-GAD 65, anti-IA2, anti-islet cell, anti-insulin

IL2 receptor saturation at investigator's discretion

PRA: panel reactive antibodies

Only if hospitalized within the past week

* Only if negative at Screening II

CGMS: continuous glucose monitoring system at Screening A², 1 year after first transplant, 1 year after final transplant

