#### **10.1.1. Definitions**

The following definitions will be applied consistently to the safety analysis:

Baseline (Clinical Labs, Physical Examinations)	The baseline value will be the result collected at the immediate pre-transplant work-up visit, if scheduled, or the most recent screening visit prior to the islet transplant where the lab/examination was scheduled.
Baseline (Vital Signs)	The baseline value will be the result collected at the immediate pre-transplant work-up visit. If this assessment was not obtained, then the most recent value obtained for

	the specific parameter prior to the islet infusion will be used as the baseline value.
Baseline (ECG parameters)	The baseline value will be the most recent pre-transplant value obtained.
Change from baseline	Value at the time point – value at baseline
Treatment-emergent	Any safety assessment that occurred at the onset of or after start of the first islet infusion, up to the end of 1-year follow-up after the last infusion.

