#### 10.1.5. Analyses of Adverse Events

Adverse events will be coded to the Medical Dictionary for Regulatory Activities (MedDRA) preferred terms (PT) and system organ classes (SOC) using version 17.0 or higher. All tabular AE summaries will be for treatment-emergent adverse events (TEAE). For all percentages, the number of patients in the ITT population will comprise the denominator.

An overall summary table will be developed to report, across the total safety population and by number of transplants received, starting from the day of first islet cells infusion to the end of 1-year follow-up after the last transplant, the total number of events and the number and percent of patients having at least one event and those related to treatment in the following categories:

a. Procedure Related Events

The incidence and severity of adverse events related to the islet infusion procedure including:

- Bleeding (> 2 g/dl decrease in hemoglobin concentration) identified within 24 hours post transplant.

- Portal vein thrombosis, branch or main, detected by ultrasound by the end of Day 7 (or on the first visit post-transplant if it does not fall on Day 7 exactly).
- Biliary puncture identified within 24 hours post transplant.
- Wound complication (infection or subsequent hernia) identified by the end of Day 7 (or on the first post-transplant visit if it does not fall on Day 7 exactly).
- Increased transaminase levels (> 5 times upper level of normal) identified by the end of Day 30 (or on the post-transplant visit that is closest to Day 30 if it does not fall on Day 30 exactly).

b. Immunosuppression/study drug Related Events

The incidence and severity of adverse events related to immunosuppression and/or the study drug (islets), including:

- Allergy
- Reduction in GFR (> 25% reduction in estimated GFR from baseline by Cockcroft and Gault formula:

$$eC_{Cr} = \frac{(140 - \text{Age}) \times (\text{Weight in kilograms}) \times [0.85 \text{ if Female}]}{72 \times (\text{Serum Creatinine in mg/dL})}$$

- Increase in urinary albumin excretion
- New onset microalbuminuria (albumin > 30 mg/day confirmed by 24 hour urine collection) in patients who were previously within normal limits
- For those patients with baseline microalbuminuria (30-300 mg/day), new onset overt albuminuria (greater than 300 mg/day confirmed by 24 hour urine collection)
- Sensitization evidenced by increase in PRA by at least 20% relative to baseline

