### 10.3. Clinical Laboratory Tests

All treatment-emergent abnormal values as determined based upon the normal values provided by the central laboratory will be listed with relevant patient information. In addition, for those tests that have potentially clinically significant (PCS) criteria, all PCS treatment-emergent values will be identified. The following PCS criteria will be used:

Clinical Chemistry Variable	PCS Criteria
Albumin	<2 g/dL
Alkaline phosphatase	> 5.0 – 20.0 x ULN*
Amylase	>2.0 – 5.0 x ULN
Calcium	<7.0 – 6.0 or >12.5 – 13.5 mg/dL
Carbon dioxide	<11 – 8 mmol/L
Cholesterol (total)	>400 – 500 mg/dL
Creatinine	>1.5 x ULN
Potassium	<3.0 - 2.5 or >6.0 - 7.0 mmol/L
PRA	> 20%**
Serum aspartate aminotransferase [SGOT (AST)]	>5.0 – 20.0 x ULN
Serum alanine aminotransferase [SGPT (ALT)]	>5.0 – 20.0 x ULN
Sodium	<130 - 120 or >155 - 160 mmol/L
Total bilirubin	>3.0 – 10.0 x ULN
Hemoglobin (urine)	Present
Albumin (urine)	>30 or 300 mg/24 hrs depending on baseline level***
Total protein (urine)	1.0 – 3.0 g/24 hrs

Clinical Chemistry Variable	PCS Criteria
Hemoglobin	< 8.0 – 6.5 g/dL
WBC Neutrophils/granulocytes	<1.0 – 0.5 x 10  /L
Platelets	<50 – 25 x 10  /L

\*LLN=Lower Limit of Normal; ULN=Upper Limit of Normal

\*\*Post allogeneic transplant

\*\*\*See safety endpoints in Section 2.7.1b.

For hematology and clinical chemistry laboratory parameters, actual values at Baseline and each follow-up visit will be summarized. The change from baseline values will be summarized at each visit. If repeated samples are performed for any scheduled time point, the first non-missing assessment for that time point will be used in these analyses.

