Listing of Concomitant Medication Use of Patients with Serious Adverse Events, Adverse Events Leading to Premature Discontinuation, and Death

Total # of Tx	Subj. No.	Adverse Event System Organ Class/ Preferred Term	Study days of onset [1]	Date of onset	Discontinued because of this AE?	Drug Class/ Preferred Drug Name	Dosing/ Frequency	Start date/ End date	Trough level [2] before dosing change
1	XXX	XXXXXXXXXXXXXXXXX/ XXXXXXXXXXXXXXXXX	XXX	XXX	XXX	XXXXXXXXXX/ XXXXXXXXXX	XXXXXX/ XXXXXX etc.	XXXXX/ XXXXX	
						XXXXXXXXXX/ XXXXXXXXXX	XXXXXX/ XXXXXX	XXXXX/ XXXXX	XXX
							XXXXXX/ XXXXXX etc.	XXXXX/ XXXXX	XXX
	etc.					etc.			
2	XXX	XXXXXXXXXXXXXXXXX/ XXXXXXXXXXXXXXXXX		XXX	XXX	XXXXXXXXXX/ XXXXXXXXXX	XXXXXX/ XXXXXX	XXXXX/ XXXXX	
	etc.					etc.			

[1] Relative to the day of the initial transplant.  
 [2] Only applicable to immunosuppression regimens.

XXXXXXXXXXXX.sas, DDMMYYYY:HHMM

TABLE 14.3.10  
 Hematology - Hemagram - Actual and Change from Baseline Results

<PAGE 1 FORMAT>

Transplant #	Parameter Name (SI Units)	Actual						Change from Baseline					
		n	Mean	SD	Med	Min	Max	n	Mean	SD	Med	Min	Max
Tx 1 (N=X)													
Baseline [1]	RBC (units)	X	XX	XX	XX	XX	XX						
	Hematocrit (units)	X	XX	XX	XX	XX	XX						
	Hemoglobin (units)	X	XX	XX	XX	XX	XX						
	Platelet Count (units)	X	XX	XX	XX	XX	XX						
Day 1 [2]	RBC (units)	X	XX	XX	XX	XX	XX	X	XX	XX	XX	XX	XX
	Hematocrit (units)	X	XX	XX	XX	XX	XX	X	XX	XX	XX	XX	XX
	Hemoglobin (units)	X	XX	XX	XX	XX	XX	X	XX	XX	XX	XX	XX
	Platelet Count (units)	X	XX	XX	XX	XX	XX	X	XX	XX	XX	XX	XX
Week 1	RBC (units)	X	XX	XX	XX	XX	XX	X	XX	XX	XX	XX	XX
	Hematocrit (units)	X	XX	XX	XX	XX	XX	X	XX	XX	XX	XX	XX
	Hemoglobin (units)	X	XX	XX	XX	XX	XX	X	XX	XX	XX	XX	XX
	Platelet Count (units)	X	XX	XX	XX	XX	XX	X	XX	XX	XX	XX	XX
Etc.													

[1] Baseline is always the value before the initial transplant.

[2] Day 1 assessments were obtained during 24 hours post-transplant during the Treatment Phase (in-clinic).

XXXXXXXXXX.sas, DDMMYYYY:HHMM

TABLE 14.3.10  
 Hematology - Hemagram - Actual and Change from Baseline Results

<PAGE 2 FORMAT>

Transplant #	Parameter Name (SI Units)	Actual						Change from Baseline					
		n	Mean	SD	Med	Min	Max	n	Mean	SD	Med	Min	Max
Tx 2 (N=X)													
Day 1	RBC (units)	X	XX	XX	XX	XX	XX	X	XX	XX	XX	XX	XX
	Hematocrit (units)	X	XX	XX	XX	XX	XX	X	XX	XX	XX	XX	XX
	Hemoglobin (units)	X	XX	XX	XX	XX	XX	X	XX	XX	XX	XX	XX
	Platelet Count (units)	X	XX	XX	XX	XX	XX	X	XX	XX	XX	XX	XX

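### SAP laboratory tables measure change after the second and third infusions from before the first transplant and, for every infusion, keep only the first sample per time point, so acute changes are blurred

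*SAP*

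**What the plan says.** **Baseline.** The note to Tables 14.3.10 to 14.3.15 in SAP section 14 reads "Baseline is always the value before the initial transplant". The pages for the second and third infusion have a change-from-baseline block with Day 1 and Week 1 rows (the lipid table, 14.3.14, starts later) but no baseline row of their own. The definition in SAP 10.1.1 uses the immediate pre-transplant work-up or "the most recent screening visit prior to the islet transplant where the lab/examination was scheduled". It does not say which transplant is meant, so the shell note is the only explicit rule.

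**Several samples at one time point.** SAP 10.3 states: "If repeated samples are performed for any scheduled time point, the first non-missing assessment for that time point will be used in these analyses". The shells treat Day 1 as one row covering the 24 hours in clinic. Protocol 6.6.6 says that in those 24 hours "liver tests, amylase, lipase, and CBC will be monitored every 8 hours". The notes to Protocol 6.6.8 say "Visits 1 and 2 include 3 evaluations per week".

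**Related safety criteria.** SAP 10.1.5 defines one procedure-related event as "Bleeding (> 2 g/dl decrease in hemoglobin concentration) identified within 24 hours post transplant" and names no reference value. It defines raised transaminases against the upper limit of normal (more than 5 times, by Day 30). SAP 10.3 also lists all treatment-emergent abnormal values, shown in Table 14.3.18.

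**The concern.** One to three infusions per subject are part of the regimen, safety is in the primary objective, and the trial is meant to support a license application. A reader of the second-infusion page will take the Day 1 change to be what that infusion did. Under the shell note it is not. It is the change since before any treatment, and by then the patient has been on immunosuppression since the first infusion. The adverse event table at the end of Protocol section 4 reports anemia and leukopenia in 10 of 10 subjects of the Phase 1/2 series, so some drift in blood counts is to be expected.

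The first-sample rule is a separate matter and applies equally to the first infusion. The earliest draw after an infusion leaves the least time for a fall in hemoglobin or a rise in AST/ALT to appear. At stake is whether the by-infusion laboratory summaries can be read as evidence on acute safety.

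**Working it through.** The plan states no figure to reproduce here. The check follows the two rules through the tables.

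**1. What the change column contains.** Let H0 be hemoglobin before infusion 1, Hk the value before infusion k, and D the Day 1 value after infusion k. The table reports

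D − H0 = (D − Hk) + (Hk − H0).

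The first term is the acute effect and the second is drift. Hk has no row on the page for infusion k, so the reader cannot separate the two.

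**2. Size, using thresholds in the documents.** Exclusion applies below 13 g/dL in men and 12 in women (Protocol 6.4.2). On-treatment anemia is below 12.1 in men and 11.7 in women (SAP 10.1.5). Acute fall needed for the tabulated decrease to reach 2 g/dL:

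- Man, 13.0 before infusion 1 and 12.1 before infusion 2: drift 13.0 − 12.1 = 0.9; needed 2 − 0.9 = 1.1.
- Woman, 12.0 and 11.7: drift 0.3; needed 2 − 0.3 = 1.7.
- Man, 14.5 (illustrative) and 12.1: drift 2.4; already past 2 with no acute fall.

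**3. If the bleeding criterion borrowed this baseline (assumption).** Suppose the acute fall is normal with mean 0.5 to 1.0 and SD 0.8 g/dL; neither figure is in the documents. The share counted as a fall above 2 is 1 − Φ((2 − drift − mean)/0.8).

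| Drift since before infusion 1 | Mean 0.5 | Mean 1.0 |
|---|---|---|
| 0 (true acute share) | 3.0% | 10.6% |
| 0.5 fall | 10.6% | 26.6% |
| 1.0 fall | 26.6% | 50.0% |
| 0.5 rise | 0.6% | 3.0% |

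Downward drift would create apparent bleeds; upward drift would hide real ones.

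**4. Samples kept in the acute window.** Day 1: 24 h ÷ 8 h = 3 samples, 1 kept. Week 1: 3 evaluations, 1 kept. Together 2 of 6 enter the summaries. Protocol 6.6.7 and 6.6.8 agree on three per week in Week 1. The lowest of three values is never above the first, and the highest never below it, so the first-sample summary can only understate the extreme. If the worst value were equally likely at each of three draws (an assumption), it would be missed 2/3 of the time.

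**5. Whether the needed values exist.** Protocol 6.5.1 sends the subject for the work-up in 6.6.4 when an islet preparation becomes available, without limiting this to the first. That work-up includes CBC, AST and creatinine. The schedule in 6.6.8 adds the metabolic panel at the transplant visit, and 6.6.7 lists ALT in that panel.

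**The case against.** The strongest reply is that bleeding and liver injury are not judged from these tables.

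- SAP 10.1.5 analyzes both as procedure-related adverse events. The transaminase criterion uses no baseline.
- The rule "the first non-missing assessment for that time point will be used in these analyses" governs the by-visit summaries, not the listing of abnormal values.
- The tables also give actual values, and Tables 14.3.6 and 14.3.7 date events from the most recent transplant.
- A fixed pre-treatment baseline is legitimate for cumulative effects.

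All of this stands. A reader might infer that bleeding and transaminase rise after repeat infusions are mis-measured throughout; the documents do not support that. For bleeding, the text leaves the reference value open, and nothing says the shell baseline would be used.

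Other limits also stand. "Repeated samples" may mean unplanned re-draws, although the SAP gives no other rule for several planned draws. The size of the drift is unknown: the Phase 1/2 table gives no grade, fall in g/dL or timing, and Protocol 6.11.2 allows for a second infusion within two weeks. Two broader figures should not carry weight. That 8 of 18 Phase 1/2 infusions (44%) were repeats pools two regimens; in the group that, like this trial, added etanercept and exenatide it was 2 of 8 (25%). A count of 11 of 19 draws unused through week 11 (58%) rests on one reading of the rule, and 10 of the 19 fall in weeks 3 to 11.

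The reply does not remove the point. The actual-value columns use the same first sample. Table 14.3.1 has no bleeding or transaminase row, Table 14.3.2 runs only from the first transplant, and Tables 14.3.3 to 14.3.5 group by total transplants received. Table 14.3.18 shows a single baseline result, and hemoglobin is flagged as potentially clinically significant only below 8.0 g/dL.

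**Conclusion.** The point holds for the by-visit laboratory summaries. In Tables 14.3.10 to 14.3.13 and 14.3.15, the early changes after the second and third infusion mix drift with the acute effect. For every infusion, the first-sample rule read literally keeps 2 of the 6 CBC and liver samples in Day 1 plus Week 1. Table 14.3.14 (lipids) starts at Weeks 4-5 and does not bear on acute effects.

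The transaminase endpoint and the listing of abnormal values are not affected. The bleeding criterion has a real but narrower gap, an unstated reference value; the percentages above apply to it only under the assumed distribution and only if the shell baseline is carried over. This is descriptive safety reporting. The primary efficacy analysis is untouched, and the change is a cheap improvement, not a correction of a failed analysis.

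**What to change.** 1. On the second- and third-infusion pages of Tables 14.3.10 to 14.3.13 and 14.3.15, add change from that infusion's immediate pre-transplant value. Keep change from before the first transplant as a labeled cumulative column.
2. In SAP 10.1.5, state that the hemoglobin fall of more than 2 g/dL is measured from that infusion's pre-transplant value. Align the baseline definition in 10.1.1 with the shells.
3. Beside the first non-missing value, add the worst value per time point: lowest hemoglobin, neutrophils and platelets; highest AST, ALT and creatinine. State in 10.3 whether the repeated-sample rule covers planned multiple draws or only re-draws.

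The cost is SAP wording, extra table columns and programming. No new data are needed, because Protocol 6.6.4, 6.6.6 and 6.6.8 already schedule the samples.
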